7.2.1. Inclusion criteria

Patients must meet all of the following criteria to be eligible for the study:

1. Diagnosed with AF anytime in the baseline period or on the index date, also have definitive diagnosis of AF anytime in the baseline period, on the index date, or post-index period.
2. Prescribed one of the index OACs (apixaban, dabigatran, edoxaban, rivaroxaban or warfarin) on or after the day of AF diagnosis. The first observed prescription will be used to identify the patient's index date and treatment cohort
3. No use of the any OACs during the baseline period (the 180 days before the index date)
4. Age of 18 years or older on the index date.

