5. RATIONALE AND BACKGROUND

Atrial fibrillation (AF) is characterized by a rapid, irregular heartbeat which can cause blood to pool in the atria and increase the risk of the formation of blood clots. AF affects 0.6% to 1.6% of the general population and up to 14% in cardiovascular clinics in Japan¹⁻³. AF can be categorized into three main categories based on patient characteristics: lone atrial fibrillation – AF in the absence of overt cardiovascular disease or precipitating illness⁹; non-valvular AF (NVAF) – presence of AF without concurrent rheumatic mitral valve disease or history of mitral valve repair or prosthetic heart valve; and secondary AF-AF that occurs in the setting of acute myocardial infarction (MI), cardiac surgery, pericarditis, myocarditis, hyperthyroidism, pulmonary embolism, pneumonia, or other acute pulmonary disease. Anticoagulation therapy is important to prevent thromboembolism in patients with NVAF. Warfarin, a vitamin K antagonist, is the first oral anticoagulant approved for the treatment and prevention of thromboembolism in Japan in 1962 and it had long been the only oral anticoagulant until the first non-vitamin K antagonist oral anticoagulants (NOACs), dabigatran, was introduced with approval for NVAF treatment in March 2011, followed by rivaroxaban in January 2012, apixaban in December 2012, and edoxaban in September 2014 in Japan.

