7. RESEARCH METHODS

7.1. Study design

This is a retrospective observational study using data from the MDV database (data set from March 1st, 2011 to December 31st, 2017). Among patients registered in the database patients are selected based on the inclusion and exclusion criteria (see blow). The first observed prescription of apixaban, dabigatran, edoxaban, rivaroxaban or warfarin is used to identify the patient's index date (date of the first prescription of any OACs is defined as "index date") and treatment cohort. Study measures include: (1) for safety evaluation: major bleeding and any bleeding; (2) for effectiveness evaluation: a composite of ischemic stroke, hemorrhagic stroke or SE.

The follow-up period is variable, and will begin on the next day of the index date and continue until the earliest of the following scenarios – occurrence of target outcome event (details available in Section 8.2); discontinuation of the index OAC; switching from the index OAC; withdrawal from the database.

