7.2. Setting

This study uses data from the MDV database, which includes the data used for both inpatient and outpatient insurance claims by hospitals according to the Diagnosis Procedure Combination (DPC) procedure.

The study population will consist of adults with NVAF who are newly prescribed apixaban, dabigatran, edoxaban, rivaroxaban or warfarin. Follow-up time period starts from the next day of the index date, and ends depending on following outcomes which observed first.

1. Major bleeding when the target outcome for the analysis is major bleeding.
2. Composite of (ischemic or hemorrhagic) stroke and SE when the target outcome for the analysis is the composite endpoint.
3. Any bleeding when the target outcome for the analysis is any bleeding.
4. Discontinuation of the index OAC: The index treatment will be considered to be "discontinued" if the index OAC is not prescribed within 45 days after prescription refill date (calculated from the last refill date plus days of supply) of the index OAC, even though the patient has >1 medical encounter records after more than 45 days following the prescription refill date. The supposed prescription refill date is regarded as the last day of the follow-up for discontinued patients.
5. Switching from the index OAC: The index treatment is regarded as "switched" if non-index OAC is prescribed within 45 days after prescription refill date of the index OAC when the patient has 1> medical encounter records after more than 45 days following the prescription refill date. The switched day is regarded as the last day of the follow-up for the switched patients.

<Eliquis>

<B0661120> Safety and effectiveness evaluation of patients with non-valvular atrial fibrillation treated with

OACs: Comparison between NOACs and warfarin (CER3)

<Final ver.1.1><20180508>

6. Withdrawal from the database: The patients are regarded as “withdrawal” from the database if the index OAC is not prescribed within 45 days after prescription refill date of the index OAC and there is no data of the patient on the database after prescription refill date. The last medical encounter is regard as the last day of the follow-up for patients withdrawn from the database.

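### Treatment-naïve status does not require an observable 180-day look-back, so ongoing OAC users can enter as new users; no index date before 28 August 2011 can have a full look-back

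*Protocol*

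**What the plan says.** Protocol 7.2 describes the population as "adults with NVAF who are newly prescribed apixaban, dabigatran, edoxaban, rivaroxaban or warfarin". Three rules put this into practice.

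- **Naïve status** (protocol 7.2.1 item 3; same wording in SAP 7.1 item 3): "No use of the any OACs during the baseline period (the 180 days before the index date".
- **Index date** (protocol 7.1): "The first observed prescription of apixaban, dabigatran, edoxaban, rivaroxaban or warfarin is used to identify" the index date and the treatment cohort. The source is the MDV database, "data set from March 1st, 2011 to December 31st, 2017".
- **AF diagnosis** (protocol 7.2.1 item 1): "Diagnosed with AF anytime in the baseline period or on the index date". A code on the index day is enough.

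No visible passage asks for an encounter, a record or database entry at least 180 days before index, and none delays the first permitted index date. The eligibility criteria are not redacted. Protocol 7.9 gives a general caution about unmeasured patient background and does not mention incomplete look-back.

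**The concern.** Item 3 looks for the absence of recorded use. It does not ask whether use could have been recorded. Since protocol 7.1 sets the index at the first OAC prescription seen in the data, recorded OAC use can hardly precede it, and item 3 has little to act on unless the preceding 180 days are known to be observed. A patient already on treatment whose first database record is a refill passes items 1 to 3.

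This can happen in two ways:

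- **At the opening of the data set.** Patients already on treatment on 1 March 2011 show their first refill soon afterwards. Warfarin is described as "the first oral anticoagulant approved for the treatment and prevention of thromboembolism in Japan in 1962", so ongoing warfarin users are to be expected at that point. Dabigatran was approved only in March 2011, and the other three NOACs came later.
- **At any later date, on any OAC.** The data come from contributing hospitals only (314 as of June 2017, protocol 7.4). The documents do not say when each hospital's data begin. A patient first seen mid-treatment enters as a starter.

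The unobserved days also weaken confounding control. Most propensity-score covariates are flags set to 1 only if a baseline code exists, so unseen history is coded as absent and never appears as missing. Prior OAC use is not a covariate. An ongoing warfarin user without recorded history can be matched to a NOAC starter who truly has no comorbidity, and the 10% standardized-difference check would report balance.

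**Working it through.** The documents give no figure for this point, so there is nothing to reproduce first.

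**1. Earliest index date with a full look-back.** Inputs: data start 1 March 2011 (protocol 7.1); look-back of the 180 days before index (protocol 7.2.1 item 3).

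- 1 March 2011 + 180 days = 28 August 2011.
- Observable look-back by index date: 0 days on 1 March, 31 on 1 April, 92 on 1 June, 179 on 27 August, 180 on 28 August.
- Window length, 1 March 2011 to 31 December 2017 inclusive: 306 + 366 + 1,095 + 366 + 365 = 2,498 days (2011; 2012; 2013–2015; 2016; 2017).
- Share of dates without a full look-back: 180 / 2,498 = 7.2%. This is a share of calendar days. No patient counts by date are given.

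**2. Which drugs the early window touches.** Warfarin was approved in 1962 and dabigatran in March 2011, "followed by rivaroxaban in January 2012, apixaban in December 2012, and edoxaban in September 2014 in Japan". The last three dates all fall after 28 August 2011, so only warfarin and dabigatran can be indexed in the window, and long-standing users there are mainly on warfarin.

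**3. How far a date cut reaches.** Protocol 7.2 item 4 sets this condition for treating a patient as having stopped: "the index OAC is not prescribed within 45 days after prescription refill date (calculated from the last refill date plus days of supply". A continuous user already followed at a contributing hospital when the data open therefore has a first observed refill no later than 28 February 2011 + days of supply + 45. The documents do not give days of supply, so these are assumptions:

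| Assumed supply | Days added | Latest first observed refill |
|---|---|---|
| 30 days | 75 | 14 May 2011 |
| 60 days | 105 | 13 June 2011 |
| 90 days | 135 | 13 July 2011 |
| 135 days | 180 | 27 August 2011 |

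Any supply up to 135 days falls before 28 August 2011. Users who first appear in the database later are not reached by the cut.

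**4. What an empty baseline does to the covariates.** SAP 10.1.1 lists 25 covariates.

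- 25 − 2 (age, gender) = 23 read from baseline.
- 23 − 2 (CHADS₂, CHA₂DS₂-VASc) = 21 binary flags, all 0 if there is no baseline record.
- CHA₂DS₂-VASc by protocol Table 1, maximum: 1 + 1 + 1 + 1 + 2 + 1 + 2 = 9 (heart failure, hypertension, diabetes, vascular disease, age, sex, prior stroke/TIA/thromboembolism).
- With no baseline diagnosis only age and sex can score: 2 + 1 = 3.

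**5. What it does to the exclusions.** Of the seven exclusions in protocol 7.2.2, numbers 2 to 5 look only at the baseline period. With no record there, these four have nothing to act on.

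**The case against.** **Index-date codes may count.** The opening sentences of protocol 7.3 and SAP 8.4 refer to information from the index date as well as the baseline period. If codes entered on the index day counted, a patient first seen that day could carry diagnoses, and the figures of 21 of 25 and 3 of 9 would not hold. The specific text points the other way: item 3 places baseline before the index date, item 1 names the two separately, and each flag's definition is confined to the baseline period. The general sentences are explained by variables such as age, sex and physician specialty, which are taken at index. The figures stand on the definitions as written.

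**Exclusion 1 is a partial backstop.** It also covers the post-index period, so some valve patients missed by exclusion 4 may be caught later. That is true, but it gives no cover for exclusions 2, 3 and 5, and none for prior OAC use.

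**The date cut is incomplete.** A patient whose first record is an index prescription in 2015 still enters with no look-back. Even the proposed sensitivity analysis does not show that prescribing was captured throughout the 180 days. Both points stand, so the cut should not be described as guaranteeing an observed look-back for each patient.

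**No effect size is shown, and redacted text may hold related analyses.** The first part is correct. The second could apply to sensitivity analyses but not to the eligibility criteria, which are visible.

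**Conclusion.** The gap is real and should be fixed before analysis. Followed as written, the criteria admit ongoing users as new starters. In the window from 1 March to 27 August 2011 (180 of 2,498 days) no patient can have a full look-back, and the ongoing users admitted there fall mainly in the warfarin arm. Patients first seen mid-treatment later can enter in any cohort. The propensity score cannot correct this, because prior OAC use is not in it and its other inputs are truncated for the same patients.

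The dates and the covariate counts follow directly from the documents. The reach of the date cut rests on assumed supply lengths. The direction of bias is unknown: patients who already tolerate treatment may have a lower hazard, while under-recorded comorbidity may hide a higher one. No patient count and no shift in hazard ratio is claimed, because the documents do not allow either.

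**What to change.** 1. In the primary analysis, accept only index dates on or after 28 August 2011. Keep the index at the first observed prescription, so that a patient whose first one falls earlier is dropped and not re-indexed at a later one. State the rule in protocol 7.2.1 and SAP 7.1, and say that it ensures only that the data set had been open for 180 days.
2. Unless redacted text already plans it, add a sensitivity analysis limited to patients with at least one database record 180 or more days before index. Report the number removed per arm by each of steps 1 and 2.
3. List incomplete look-back as a limitation in protocol 7.9.

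The cost is one date filter, one sensitivity run and some wording. By the protocol's approval dates the cut removes no rivaroxaban, apixaban or edoxaban patients. For those three contrasts it removes only warfarin patients indexed before the NOAC was approved. Some true new users of warfarin and dabigatran from March to August 2011 are lost. The sensitivity analysis also drops true starters first seen at index, which is why it is not proposed as primary.

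A separate drafting point, on which nothing above depends: SAP 7, 7.1, 8.4, 10.1.4 and 10.1.5 name only apixaban, edoxaban and warfarin and should be reconciled with the four planned NOAC comparisons.

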7.2.2. Exclusion criteria

Patients meeting any of the following criteria will not be included in the study:

1. Having a diagnosis of valvular atrial fibrillation, post-operative atrial fibrillation, rheumatic atrial fibrillation or mechanical-valvular atrial fibrillation during the baseline and post-index period
2. Having a cardiac surgery procedure record during the baseline period
3. Having a joint replacement procedure record during the baseline period
4. Having a procedure of prosthetic heart valve during the baseline period
5. Having a diagnosis of venous thromboembolism during the baseline period
6. Female patients with pregnancy during the follow-up period
7. Patients prescribed “off-label” doses of OACs (per Japanese package insert of each OAC) or patients treated with OAC but in “off-label” or “contraindicated” manners.

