Peripheral arterial disorder diagnosis in baseline	Baseline period	Dichotomous variable equals 1 if there are ≥1 diagnoses for peripheral arterial disorder ICD-10 or disease codes during the baseline period.
Myocardial infarction diagnosis in baseline	Baseline period	Dichotomous variable equals 1 if there are ≥1 diagnoses for myocardial infarction ICD-10 or disease codes during the baseline period.
Hyperthyroidism or thyrotoxicosis in baseline	Baseline period	Dichotomous variable equals 1 if there are ≥1 diagnoses for hyperthyroidism ICD-10 or disease codes during the baseline period.
Stroke, TIA or SE diagnosis in baseline	Baseline period	Dichotomous variable equals 1 if there are ≥1 diagnoses for Stroke, TIA or systemic embolism ICD-10 or disease codes during the baseline period.
Renal dysfunction diagnosis in baseline	Baseline period	Dichotomous variable equals 1 if there are ≥1 diagnoses for renal dysfunction ICD-10 or disease codes during the baseline period.
Liver dysfunction diagnosis in baseline	Baseline period	Dichotomous variable equals 1 if there are ≥1 diagnoses for liver dysfunction ICD-10 or disease codes during the baseline period.
Bleeding diagnosis in baseline	Baseline period	Dichotomous variable equals 1 if there are ≥1 diagnoses for bleeding ICD-10 or disease codes during the baseline period.
Hypertension diagnosis in baseline	Baseline period	Dichotomous variable equals 1 if there are ≥1 diagnoses for hyper tension ICD-10 or disease codes during the baseline period.
Diabetes mellitus diagnosis in baseline	Baseline period	Dichotomous variable equals 1 if there are ≥1 diagnoses for diabetes mellitus ICD-10 or disease codes during the baseline period.

<Eliquis>

<B0661120> Safety and effectiveness evaluation of patients with non-valvular atrial fibrillation treated with OACs: Comparison between NOACs and warfarin (CER3)

<Final ver.1.1><20180508>

Cancer diagnosis in baseline	Baseline period	Dichotomous variable equals 1 if there are ≥ 1 diagnoses for diabetes mellitus ICD-10 or disease codes during the baseline period.
Treated with antiplatelet drug in baseline	Baseline period	Dichotomous variable equals 1 if there are ≥ 1 prescriptions of antiplatelet drug ATC or receipt codes during the baseline period.
Treated with NSAIDs in baseline	Baseline period	Dichotomous variable equals 1 if there are ≥ 1 prescriptions of NSAIDs ATC or receipt codes during the baseline period.

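### The index date lies in neither the baseline window nor follow-up, so comorbidities and exclusion conditions recorded only on that day are missed

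*Protocol*

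**What the plan says.** - **Baseline window.** It is defined once, in inclusion criterion 3 of Protocol 7.2.1: "No use of the any OACs during the baseline period (the 180 days before the index date".
- **AF diagnosis.** Inclusion criterion 1 accepts a patient "Diagnosed with AF anytime in the baseline period or on the index date", who must "also have definitive diagnosis of AF anytime in the baseline period, on the index date, or post-index period". The index date is thus listed as a third window beside baseline and post-index. Criterion 2 allows the OAC to be prescribed on the day AF is diagnosed.
- **Follow-up.** Protocol 7.1 says that it "will begin on the next day of the index date". Protocol 7.2 agrees: "Follow-up time period starts from the next day of the index date". SAP 8.1 also leaves the index date out of the ischemic stroke, hemorrhagic stroke and SE outcomes.
- **Covariates.** Table 1 in Protocol 7.3 takes five variables at the index date: sex, age, physician specialty, hospital size and inpatient status. It takes both risk scores from baseline. Each comorbidity, co-medication and cardioversion flag is confined to baseline; the prior-stroke flag, for example, needs one or more "diagnoses for Stroke, TIA or systemic embolism ICD-10 or disease codes during the baseline period". SAP 8.4 repeats the flag definitions, and SAP 10.1.1 enters flags and scores in the propensity score as baseline items.
- **Exclusions.** Criteria 2 to 5 in Protocol 7.2.2 are confined to baseline, for example "Having a diagnosis of venous thromboembolism during the baseline period". Criterion 1 covers "mechanical-valvular atrial fibrillation during the baseline and post-index period", again without naming the index date. SAP 7.1 repeats these criteria.
- **General sentences.** The openings of Protocol 7.3 and SAP 8.4 both mention the index date alongside the baseline period as a source of patient characteristics.

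**The concern.** The plan admits patients who are diagnosed and treated on the same day, but does not look at that day for their other conditions. Heart failure, hypertension, diabetes or stroke first coded at that visit or admission counts as absent. A stroke coded only on that day is neither history nor outcome.

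The later steps cannot reveal this. Balance is judged by standardized differences below 10% on the recorded values, and if they pass, the Cox model contains only the index OAC. IPTW uses the same covariates, so it is not an independent check. If index-day-only conditions are more common in one arm, the difference stays in the hazard ratio unseen. A VTE, joint replacement, cardiac surgery or prosthetic valve recorded only on the index date also does not trigger the exclusion written for it.

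**Working it through.** The plan gives no figure on this point, and the SAP 6.2 sample sizes do not depend on it. The check is one of windows, followed by an illustration of size.

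**1. Windows, with the index date as day 0**

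- Baseline: days −180 to −1 (Protocol 7.2.1).
- Follow-up: day +1 onward (Protocol 7.1 and 7.2).
- Days from −180 onward that fall in neither: day 0 only.
- With covariates and exclusions taken over days −180 to 0: none uncovered, and no overlap with follow-up.

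**2. What a record on day 0 alone does under the text**

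| Item | Result |
|---|---|
| AF | Counted (inclusion 1) |
| Comorbidity, co-medication, cardioversion | Coded absent |
| CHADS2, CHA2DS2-VASc | Diagnosis components missed; age and sex still count |
| Exclusions 2 to 5 | Not triggered |
| Exclusion 1 | Not triggered by that record; a repeat code later would exclude |
| Stroke or SE outcome | Not counted |

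A condition that also has a code on days −180 to −1 is captured as intended.

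**3. Illustrative size**

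The documents give no index-day prevalences, so every input here is an assumption. True prior-stroke prevalence p is 25% on warfarin and 18% on a NOAC. A share s of it, equal in both arms, is recorded only on day 0. Prior stroke multiplies the outcome hazard by k = 2 or 3. The true hazard ratio is 1.

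- Hidden prevalence among patients coded absent: h = p·s / (1 − p(1 − s)). For s = 40%: warfarin 0.100/0.850 = 11.8%; NOAC 0.072/0.892 = 8.1%.
- Observed hazard ratio among patients coded absent (an approximation for rare events): [1 + (k − 1)h_NOAC] / [1 + (k − 1)h_warfarin]. For s = 40%, k = 2: 1.081/1.118 = 0.967.
- Whole matched cohort, with recorded stroke balanced at the NOAC level r = 0.18(1 − s): effective warfarin prevalence P = r + (1 − r)h_warfarin, and ratio [1 + 0.18(k − 1)] / [1 + P(k − 1)]. For s = 40%: r = 0.108 and P = 0.108 + 0.892 × 0.118 = 0.213; for k = 2: 1.18/1.213 = 0.973.

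| s | h warfarin | h NOAC | Coded absent, k = 2 / 3 | Whole cohort, k = 2 / 3 |
|---|---|---|---|---|
| 20% | 6.2% | 4.2% | 0.981 / 0.964 | 0.985 / 0.975 |
| 40% | 11.8% | 8.1% | 0.967 / 0.940 | 0.973 / 0.954 |
| 60% | 16.7% | 11.6% | 0.957 / 0.925 | 0.962 / 0.936 |

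**4. Sensitivity to the assumptions**

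Setting the hidden prevalence among patients coded absent directly gives, within that group:

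- 3% against 2%, k = 1.5: 1.010/1.015 = 0.995.
- 20% against 10%, k = 3: 1.20/1.40 = 0.857.
- The same pairs with the arms reversed: 1.005 and 1.167.
- Equal prevalences: exactly 1, no bias.

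**The case against.** The strongest reply is that the text is not uniform. The openings of Protocol 7.3 and SAP 8.4 both name the index date, and the programmers may already count it. That is possible, but those sentences are general, and the definitions beneath them assign individual variables to a window. SAP 8.4 gives no window for the two scores, but Table 1 and SAP 10.1.1 place them at baseline. Two analysts could code day 0 differently, so the passages need reconciling in any case.

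A second reply is that strictly pre-index covariates are a defensible choice. This stands for some items. Day-level dates cannot order an index-day bleed against the first dose, and index-day heparin or cardioversion may belong to the same treatment decision as the OAC. It is weaker for comorbidities such as hypertension, diabetes or heart failure, and it does not explain why AF alone is counted on day 0.

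Third, Protocol 7.9 already concedes claims misclassification and residual differences between cohorts. It does not mention this window, which, unlike unmeasured confounding, can be repaired with data in hand.

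Some stronger inferences fail. AF is not scored absent: it is counted on day 0 and is not a propensity-score covariate. Nor does every patient started for a same-day VTE stay in the cohort. Such a patient also needs an AF diagnosis by that day, and exclusion 7, on off-label or contraindicated use, states no window. It is plausible that OAC starts cluster on the day comorbidity is first coded, but the documents neither say so nor count such patients.

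**Conclusion.** The gap is real on the plan's own definitions. Day 0 is uncovered for comorbidity flags, for the diagnosis components of both risk scores, and for exclusions 2 to 5. Exclusion 1 shares the gap only when no later code appears.

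Its effect is not established. In the prior-stroke illustration the whole-cohort hazard ratio moves by 1.5% to 6.4% (factors 0.985 to 0.936), which rests on assumed prevalences, an equal index-day-only share in both arms and an assumed hazard multiplier. Other covariates could add to this or offset it. A reader might infer that the gap favours the NOACs. That follows only from assuming more hidden prior stroke on warfarin; with the imbalance reversed the shift reverses, and with equal index-day-only prevalence there is none. This is a cheap improvement to the specification, not evidence that the comparisons are biased in a known direction.

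**What to change.** 1. In Protocol 7.2.2 and 7.3 and SAP 7.1, 8.4 and 10.1.1, set the window for comorbidity diagnoses, risk-score components and exclusions 1 to 5 to days −180 to 0, counting the index date as day 0. Exclusion 1 keeps its post-index part.
2. Leave the rule of no OAC use as days −180 to −1, and leave follow-up starting on day +1.
3. For bleeding history, co-medication (including heparins) and cardioversion, keep days −180 to −1 in the main analysis and run days −180 to 0 as a sensitivity analysis.
4. Reword the openings of Protocol 7.3 and SAP 8.4 to agree with the variable-level definitions. If day 0 is already counted in the programs, say so.
5. Report, by cohort, how many patients have each condition recorded only on day 0. This replaces the assumed prevalences above with observed ones.

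The cost is a change of definition and a re-run of the flags, exclusions, matching and weighting on the same extract. The downside is that some index-day codes may be provisional diagnoses; comparing results under both windows would show whether that matters.
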